#### 4.8.2. Laboratory Data

Clinical laboratory values will be expressed using SI units.

A tabulation (n, %) by treatment group and overall of whether a subject had a clinical abnormality at any time, and a listing of clinical abnormalities, for all identified laboratory abnormalities, will be generated.

Tabulation of actual value and change from baseline to each on study evaluation will be presented for each clinical laboratory parameter, including hematology and clinical chemistry. In the event of repeat values, the last non-missing value per study day/time will be used.

Continuous lab parameters will be categorized as low, medium, or high based on the value of the parameter. Shift tables for lab parameters from baseline to all applicable visits will be presented.

All laboratory data will be provided in data listings.

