8. History of myocardial infarction, unstable angina, transient ischaemic attack, decompensated heart failure requiring hospitalisation, congestive heart failure (New York Heart Association Class 3 or 4), uncontrolled arrhythmias, cardiac revascularisation, stroke, uncontrolled hypertension (systolic blood pressure [BP] > 160 mmHg or diastolic BP > 100 mmHg at Screening), or uncontrolled diabetes (haemoglobin A1c > 9% or > 1 episode of severe hypoglycaemia) within 6 months of screening.

9. Clinically meaningful laboratory abnormalities at Screening, including but not limited to, the ranges below:
 - a. Absolute neutrophil count < 1000/ μ L
 - b. Platelet count < 100,000/ μ L
 - c. Haemoglobin < 9 g/dL
 - d. Creatinine \geq 1.5 mg/dL
 - e. alanine aminotransferase or aspartate aminotransferase \geq 2.5 x upper limit of normal (ULN) or bilirubin > 1.5 x ULN
10. Pregnant or lactating females.
11. Any surgical procedure requiring general anaesthesia within 1 month prior to screening, or planned elective surgery during the study.
12. History of malignant neoplasms or carcinoma in situ within 5 years prior to screening. (Subjects who are cancer-free for the previous 5 years may be enrolled. Subjects with adequately treated non-metastatic basal cell skin cancer, squamous cell skin cancer that has not recurred for at least 1 year prior to screening, or history of adequately treated cervical dysplasia/cervical intraepithelial neoplasia or cervical carcinoma in situ that has not recurred at least 3 years prior to screening may be enrolled.)
13. History of any major neurological disorders, as judged by the Investigator, or positive PML subjective symptom checklist.
14. Current or recent history of alcohol dependence or illicit drug use within 1 year prior to screening.
15. Subject is mentally or legally incapacitated at the time of Screening visit or has a history of clinically significant psychiatric disorders that would impact the subject's ability to participate in the trial according to the Investigator. Note: Subjects who have had situational depression or adjustment disorder or treated depression may be enrolled at the discretion of the Investigator.
16. Unable to attend study visits or comply with procedures.
17. Concurrent participation in any other interventional study.

Medication exclusion criteria

18. Use of topical 5-ASA or corticosteroid enemas/suppositories within 2 weeks of administration of the screening endoscopy.

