7.5 Statistical Analysis of Safety Data

The primary safety endpoint is the proportion of subjects with at least 1 AE comparing individual PTG-100 dosing groups with placebo.

The secondary endpoints (all based on comparison of individual PTG-100 dose levels to placebo) will include:

1. Frequency and type of AEs (affecting $\geq 5\%$ of subjects)
2. Proportion of subjects with at least 1 SAE
3. Number and type of SAEs
4. Frequency of AEs of special interest including serious or opportunistic infection (viral, bacterial, fungal including systemic/gut localization), allergic/drug reactions, immune system disorders, and suspected PML
5. Clinically significant changes in safety labs, ECGs, or physical examination findings (including vital signs).

Continuous safety data will be summarised with descriptive statistics (arithmetic mean, standard deviation [SD], median, minimum, and maximum) by dose level. Categorical safety data will be summarised with frequency counts and percentages by dose level. Adverse events will be coded using the most current Medical Dictionary for Regulatory Activities available, which will be indicated in the Data Management Plan. A by-participant AE data listing, including verbatim term, preferred term, system organ class, treatment, severity, and relationship to study drug, will be provided. The number of participants experiencing treatment-emergent AEs (TEAEs) and number of individual TEAEs will be summarised by treatment group, system organ class, and preferred term. The TEAEs will also be summarised by severity and by relationship to study drug.

Laboratory evaluations, vital signs assessments, and ECG parameters will be summarised by treatment group and protocol-specified collection time point. A summary of change-

from-baseline at each protocol-specified time point by treatment group will also be presented.

Clinically significant changes in physical examinations will be listed for each participant and described in the text of the Clinical Study Report.

Medical history will be listed by subject.

Concomitant medications will be listed by participant and coded using the most current World Health Organization drug dictionary.

Further details regarding presentation and analysis of safety data will be detailed in the SAP.

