APPENDIX E - BLOOD SAMPLING SUMMARY

Purpose	Maximum Blood Volume per Sample (mL)	Maximum Number of Blood Samples	Maximum Total Volume (mL)
Hepatitis screen	3.5	1	3.5
Pregnancy tests	3	3	9
Pharmacokinetic sampling	4	12	48
Pharmacodynamic sampling	2	7	14
Haematology	4	7	28
Clinical laboratory tests	3.5	7	24.5
Coagulation	1.8	7	12.6
Anti-drug antibody test	3	5	15
Immunologic analysis	3	1	3
Total			157.6

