**Table 1 Schedule of Assessments**

	Screening	Random- ization Period	Treatment								Follow up	Early Termination 
	Days -35 to -7	Day -7 to Day -1	Day 0 (pre- dose) 	Day 0 (dosing, post-dose)	Day 14 ±3 days	Day 28 ±3 days	Day 42 ±3 days	Day 56 ±3 days	Day 70  ±3 days	Day 84 ±3 days	Day 112 ±7 days	
Informed Consent	X											
Demographics	X											
Medical History	X											
Prior and Concomitant Medications 	X		X	X	X	X	X	X	X	X	X	X
Inclusion/Exclusion	X											
Height	X											
Weight	X		X		X	X	X	X		X	X	X
Physical Examination 	X		X	X	X	X	X	X		X	X	X
Vital Signs 	X		X	X 	X	X	X	X		X	X	X
12-lead ECG 	X		X 		X			X		X	X 	X
Laboratory: Haematology, Coagulation, Serum Chemistry 	X		X		X	X		X		X	X	X
Stool C.diff , Culture, and Ova and Parasites	X											
Urinalysis (dipstick and microscopy if abnormal)	X		X		X	X		X		X	X	X
PML Neurological Assessment 	X		X		X	X	X	X	X	X	X	X

	Screening	Random-ization Period	Treatment								Follow up	
	Days -35 to -7	Day -7 to Day -1	Day 0 (pre-dose) 	Day 0 (dosing, post-dose)	Day 14 ±3 days	Day 28 ±3 days	Day 42 ±3 days	Day 56 ±3 days	Day 70  ±3 days	Day 84 ±3 days	Day 112 ±7 days	Early Termination 
Hepatitis B & C; TB Test	X											
Serum Pregnancy (WOCBP)	X									X	X	X
Sigmoidoscopy	X 									X		X
Colonic Biopsy	X 									X		X
Mayo Score 	X 				X	X	X	X	X	X	X	X
JCV Antibody Testing 	X 											
Confirmation of Eligibility			X									
Randomisation 		X										
Adverse Events			X	X	X	X	X	X	X	X	X	X
IBDQ			X							X		X
Faecal Calprotectin			X				X			X	X	X
Urine Pregnancy (WOCBP)			X		X	X	X	X				
PK Blood Collection 			X	X 	X	X	X	X		X 		X 
PD Blood Collection 			X	X 	X	X	X	X		X 		X 
ADA Testing			X			X		X		X	X	X
Exploratory Immunologic Assessment Blood Sample 			X									
IP Administration 				X	X	X	X	X	X	X		

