ADA = anti-drug antibodies; AE = adverse event; ECG = electrocardiogram; IBDQ = Inflammatory Bowel Disease Questionnaire; IP = investigational product; JCV= John Cunningham virus; PD = pharmacodynamics; PK = pharmacokinetics; PML = progressive multifocal leukoencephalopathy; TB = tuberculosis; WOCBP = women of childbearing potential.

 All predose procedures should be completed prior to dosing.

 Day 70 AE monitoring will be obtained via phone call and data to calculate rectal bleeding and stool frequency subscores will be obtained.

 Procedures to be performed within 10 days of Early Termination.

 All prior medications taken within 3 months before screening should be recorded.

 Complete physical examinations should be conducted at Screening, Day 84, Day 112, and/or Early Termination. Directed physical examinations should be conducted at other time points. The Day 0 postdose examination will occur 4 hours postdose.

 Participants should be rested in a supine or semi-recumbent position for  $\geq 3$  minutes prior to recording of ECGs and vital signs. The ECGs and vital signs should be assessed prior to blood draws. Temperature by oral, axillary, or tympanic route may be permitted provided the same route is used for the participant throughout the study.

 Vital signs will be done at 1, 2, and 4 hours  $\pm$  20 minutes postdose following the first dose of study drug.

 Predose (baseline) ECGs should be repeated 3 times with 1- to 2-minute intervals between ECG readings, all within 2 hours prior to dosing.

 ECG only to be performed if previously abnormal.

 Laboratory samples collected at Screening and on Day 0 (predose), Day 28, Day 84 (or Early Termination), and Day 112 MUST be after the participant has FASTED from all food and drink except water for  $\geq 8$  hours (except for any dietary requirements that are part of sigmoidoscopy prep). Chemistry Panel at these fasting visits will include cholesterol and glucose analytes. All other non-fasting visits will have Chemistry Panel completed without cholesterol and glucose analytes. See [Appendix B](#) for list of analytes assessed.

 PML Assessment Questionnaire (see [Appendix D](#)). If the Screening PML assessment was performed within 14 days of Day 0, it will not need to be repeated on Day 0.

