### 4.8.1. Adverse Events

The primary safety endpoint is the proportion of subjects with at least 1 AE comparing individual PTG-100 dose groups with placebo.

Secondary endpoints (all based on comparison of individual PTG-100 dose levels to placebo) will include:

- Frequency and type of AEs (affecting  $\geq 5\%$  of subjects)
- Proportion of subjects with at least 1 SAE
- Number and type of SAEs
- Frequency of adverse events of special interest (AESI) including serious or opportunistic infection (viral, bacterial, fungal including systemic/ gut localization), allergic/ drug reactions, immune system disorders, and PML or new onset neurologic symptoms

Adverse events will be coded using the Medical Dictionary for Regulatory Activities (MedDRA) and displayed in tables and listings using System Organ Class (SOC) and Preferred Term.

Analyses of adverse events will be performed for those events that are considered treatment emergent, where treatment emergent is defined as any adverse event with onset after the administration of study medication through the end of the study visit or any event that was present at baseline but worsened in intensity or was subsequently considered drug-related by the investigator through the end of the study.

Adverse events are summarized by subject incidence rates, therefore, in any tabulation, a subject contributes only once to the count for a given adverse event (SOC or preferred term).

The number and percentage of subjects

- with any treatment-emergent adverse event
- with any treatment-emergent adverse events assessed by the Investigator as related to treatment (definite, probable, or possible relationship)
- with any treatment-emergent serious adverse event
- with treatment-emergent adverse events by severity
- with adverse events affecting  $\geq 5\%$  of subjects within any treatment group across both stages of the study
- with AESI

will be summarized by treatment group and overall. In addition, all active groups will be pooled in the summaries for comparison to placebo. In these tabulations, each subject will contribute

only once (i.e., the most related occurrence or the most intense occurrence) to each of the incidence rates in the descriptive analysis, regardless of the number of episodes.

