Table 14.3.1.8	Summary of Adverse Events Leading to Study Withdrawal by System Organ Class, Preferred Term and Treatment Group (Safety)
Table 14.3.1.9	Summary of Treatment-Emergent Adverse Events with a Fatal Outcome by System Organ Class, Preferred Term and Treatment Group (Safety)

*Listings of Deaths, Serious Adverse Events and Other Significant Events (CSR Section 14.3.2)*

Table 14.3.2.1	Listing of Subject Deaths
Table 14.3.2.2	Listing of Serious Adverse Events
Table 14.3.2.3	Listing of Adverse Events Leading to Withdrawal or Death

*Abnormal Laboratory Value Tables and Listings (CSR Section 14.3.4)*

Table 14.3.4.1.1	Summary of Clinical Laboratory Abnormalities: Hematology (Safety)
Table 14.3.4.1.2	Summary of Clinical Laboratory Abnormalities: Chemistry (Safety)
Table 14.3.4.1.3	Summary of Clinical Laboratory Abnormalities: Urinalysis (Safety)
Table 14.3.4.1.4	Summary of Clinical Laboratory Abnormalities: Coagulation (Safety)
Table 14.3.4.2.1	Listing of Clinical Laboratory Abnormalities: Hematology (Safety)

Table 14.3.4.2.2	Listing of Clinical Laboratory Abnormalities: Chemistry (Safety)
Table 14.3.4.2.3	Listing of Clinical Laboratory Abnormalities: Urinalysis (Safety)
Table 14.3.4.2.4	Listing of Clinical Laboratory Abnormalities: Coagulation (Safety)

*Other Safety Information (CSR Section 14.4)*

Table 14.4.1.1	Clinical Laboratories: Hematology Actual Values and Changes Over Time on Study (Safety Population)
Table 14.4.1.2	Clinical Laboratories: Chemistry Actual Values and Changes Over Time on Study (Safety Population)
Table 14.4.1.3	Clinical Laboratories: Urinalysis Actual Values and Changes Over Time on Study (Safety Population)
Table 14.4.1.4	Clinical Laboratories: Coagulation Actual Values and Changes Over Time on Study (Safety Population)
Table 14.4.2.1	Clinical Laboratories: Shifts from Baseline Over Time on Study for Hematology (Safety Population)
Table 14.4.2.2	Clinical Laboratories: Shifts from Baseline Over Time on Study for Clinical Chemistry (Safety Population)
Table 14.4.2.1	Clinical Laboratories: Shifts from Baseline Over Time on Study for Urinalysis (Safety Population)
Table 14.4.2.2	Clinical Laboratories: Shifts from Baseline Over Time on Study for Coagulation (Safety Population)
Table 14.4.3	Vital Signs: Actual Values and Changes Over Time on Study (Safety Population)
Table 14.4.4	Shifts from Baseline Over Time on Study for Physical Examination Findings (Safety Population)

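### The laboratory abnormality tables count abnormalities at any time, pre-dose samples included, so each arm's per-subject incidence mixes pre-existing with on-treatment findings and loses sensitivity to a drug effect

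*SAP*

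**What the plan says.** SAP 4.8.2 plans a count and percentage, by treatment group and overall, of "whether a subject had a clinical abnormality at any time". The outputs are Tables 14.3.4.1.1 to 14.3.4.1.4 (haematology, chemistry, urinalysis, coagulation). Their titles in SAP 7.1, such as "Summary of Clinical Laboratory Abnormalities: Hematology (Safety", add no post-baseline or treatment-emergent limit. SAP 4.8.2 does not define what makes a value a clinical abnormality.

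SAP Table 1 (Schedule of Assessments) marks the row "Laboratory: Haematology, Coagulation, Serum Chemistry" at Screening, Day 0 predose and Days 14, 28, 56, 84 (or Early Termination) and 112. Its footnote on fasting names pre-dose samples explicitly: "Laboratory samples collected at Screening and on Day 0 (predose), Day 28, Day 84 (or Early Termination), and Day 112".

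For adverse events the SAP does set a limit (4.8.1): "Analyses of adverse events will be performed for those events that are considered treatment emergent". That includes events present at baseline that worsened.

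Protocol 7.5 lists as a secondary safety endpoint, compared between each dose and placebo: "Clinically significant changes in safety labs, ECGs, or physical examination findings (including vital signs".

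SAP 4.8.2 also plans actual values and changes from baseline at each evaluation, low/medium/high categories for continuous parameters, and shift tables from baseline to each visit.

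**The concern.** A per-subject incidence by arm is the table a reader turns to when asking how many subjects developed a laboratory abnormality on each dose. As worded, it answers a different question: how many had one at any point, including before they took study drug.

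Entry criteria leave room for such subjects. Protocol 5.2 excludes "Haemoglobin < 9 g/dL" and transaminases at or above 2.5 times the upper limit of normal, so milder departures can enter. A subject with haemoglobin of 10 g/dL at Screening that never changes would be counted if that value is flagged low. So would a subject whose raised ALT at Screening was normal at every later visit. Neither says anything about the drug.

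At stake is the table's ability to show a laboratory signal, in a trial whose first primary objective is safety and tolerability and which is the first to give this drug to patients with ulcerative colitis.

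**Working it through.** **Pre-dose share of the schedule.** The laboratory row in SAP Table 1 has these time points: Screening, Day 0 predose, Day 14, Day 28, Day 56, Day 84 or Early Termination, Day 112. That is 7. Protocol Appendix E, under "Maximum Number of Blood Samples", gives 7 each for haematology, clinical laboratory tests and coagulation, so the counts agree. Two of the 7 (2/7 = 29%) come before the first dose.

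**Does other text narrow the rule?** Elsewhere the SAP restricts or separates time: adverse events are limited to treatment-emergent ones (4.8.1), physical examination abnormalities are shown by visit (4.8.3), and ECG categories are shown at baseline and at each visit (4.8.4). Only the laboratory sentence merges all time into one count. A programmer following it would include both pre-dose samples.

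**Effect on the arm comparison.** For one parameter, let b be the share of subjects abnormal before dosing (taken as equal across arms) and e the risk of a post-dose abnormality among the rest. Then:

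- any-time incidence = b + (1 - b) × e
- difference between arms = (1 - b) × (e on drug - e on placebo)

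Neither b nor e is given in the documents, so all values below are assumptions. With e = 5% on placebo and 10% on drug:

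| b | Placebo | Drug | Difference | Ratio |
|---|---|---|---|---|
| 0% | 5% | 10% | 5 points | 2.00 |
| 20% | 0.20 + 0.80 × 0.05 = 24% | 0.20 + 0.80 × 0.10 = 28% | 4 points | 1.17 |
| 40% | 0.40 + 0.60 × 0.05 = 43% | 0.40 + 0.60 × 0.10 = 46% | 3 points | 1.07 |
| 60% | 0.60 + 0.40 × 0.05 = 62% | 0.60 + 0.40 × 0.10 = 64% | 2 points | 1.03 |

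With e = 10% and 25% the pattern is the same. The ratio of 2.50 and difference of 15 points become 1.43 and 12 points at b = 20% (28% against 40%), and 1.14 and 7.5 points at b = 50% (55% against 62.5%).

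**After restricting the count to new post-dose abnormalities.** The incidence over all subjects with baseline and post-dose values is (1 - b) × e. At b = 20% that is 0.80 × 5% = 4% against 0.80 × 10% = 8%, so the ratio is back to 2.0. The difference over all subjects is still 4 points. Dividing instead by the 80% not already in the category gives 5% against 10%, the full 5 points. A baseline row lets the reader make that step.

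**The case against.** The strongest reply is that the information is largely available elsewhere. Protocol 7.5 plans laboratory data by treatment group and time point with change from baseline, and SAP 4.8.2 delivers that together with shift tables. Protocol Appendix F treats clinically relevant adverse laboratory changes as adverse events. SAP 4.8.1 then counts each subject once per term, by arm, among treatment-emergent events. This is already a per-subject count of new or worsened laboratory findings, though one that depends on the investigator reporting the change. The reply stands in part. By-visit cells cannot be added up to a number of subjects, because one subject may appear at several visits. No planned output gives a count from the laboratory values of subjects per arm with any new post-dose abnormality.

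Two points on size also stand. If clinical abnormality means clinically significant, the open-ended laboratory exclusion in Protocol 5.2 would keep b low at Screening. If the tables have one row per parameter, baseline anaemia cannot hide a new ALT rise, and b must be judged parameter by parameter.

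A reader might infer more than the documents support:

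- **Bias against an arm.** Pre-dose abnormalities are balanced by randomisation in expectation. What is expected is attenuation, with chance imbalance adding noise.
- **Tables dominated by pre-existing disease.** No baseline prevalence is given anywhere, so this cannot be asserted.
- **Failure to analyse the protocol endpoint.** SAP 4.8.1 leaves the laboratory-change endpoint off its list of secondary safety endpoints, but no text names Tables 14.3.4.1.1 to 14.3.4.1.4 as its analysis, and the change and shift tables address it by visit.

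**Conclusion.** The point holds as a loss of sensitivity in a descriptive table. As written, the any-time rule takes in the Screening and Day 0 predose samples, and nothing else in the SAP removes them. The risk difference is attenuated by (1 - b). Under assumed new-onset risks of 5% and 10%, the ratio of 2.0 falls to 1.17 at b = 20% and 1.07 at b = 40%, with no loss at b = 0. The size rests on assumed values for b and for both risks, and on b being equal across arms.

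No formal test or decision rule uses the table, and other planned outputs recover part of the information. The change is still worth making before database lock. The wording is a single rule, the SAP already applies a comparable one to adverse events, and the table invites a reading that its present definition does not support.

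**What to change.** In SAP 4.8.2, replace the any-time condition with this rule: a subject is counted for a parameter if, at any assessment after the first dose, scheduled or unscheduled, the value falls in an abnormal category (low or high) that the subject was not in for that parameter at baseline. In addition:

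- Define clinical abnormality by those low and high categories. For urinalysis items that are not continuous, apply the same rule with normal and abnormal.
- Tabulate by parameter.
- Use as denominator the subjects with a baseline and at least one post-dose value.
- Show baseline abnormalities in a separate row, so that the percentage among subjects not already in the category can be read off.
- Amend the titles of Tables 14.3.4.1.1 to 14.3.4.1.4 to match.

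The cost is SAP wording and minor programming, with no new data. The drawback is that worsening within a category (for example, a high value going higher) is not counted, because the SAP has no finer grading than low, medium and high. It would be seen only in the change-from-baseline tables.

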#### 4.8.3. Vital Signs and Physical Examinations

Tabulation of actual value and change from baseline to each on study evaluation will be presented for all vital signs. No hypothesis testing will be conducted for vital sign data.

By-subject listings of vital sign measurements will be presented in data listings.

Physical examination results at each time point will be summarized; shifts from baseline in physical examination findings to each on study visit will also be presented. Clinically significant changes in physical examinations will be listed for each participant and described in the text of the final report.

A tabulation (n, %) of subjects with a physical examination abnormality will be presented by visit and dose group. The tabulation will be presented by body system. Subjects with no examination for a particular body system will not be included in the summary statistics for that body system. No formal statistical comparisons will be performed.

All physical examination findings will be presented in a data listing.

